11.3 Data Analyses

Data will be summarized with respect to demography and baseline characteristics, efficacy measurements, safety observations and measurements, health care resource utilization and patient global assessments. In addition, subgroup analyses will be performed by age group following the age ranges provided in the ICH Topic E11 guideline, and in details children (two classes 1 month – 5 years; 6-11 years) and adolescents (12- <18 years).

11.4 Demographic characteristics

Demographic characteristics will be summarized by treatment group using mean, standard deviation, median, percentiles for continuous variables and frequencies for categorical variables.

11.5 Study medication

Drug exposure will be summarized (using mean, standard deviation, median, percentiles) on a quarterly basis for each treatment arm and tabulated side-by-side. Any dose changes for safety reasons will be listed along with the cause.

11.6 Efficacy evaluation

Primary efficacy

The primary efficacy evaluation will be based on a treatment success rate defined in Section 4.3 Primary endpoint. The primary analysis will be based on the PP1 population.

In addition, an ITT analysis will be performed to corroborate the findings. If no composite endpoint is estimable at 1 year treatment (unavailability of serum ferritin and/or MRI determination either at baseline or after 1 year treatment), the subject is considered a treatment failure in the ITT analysis. Non-inferiority will be assessed based on the two sided 95% confidence interval $[\delta_L, \delta_U]$ of the difference $\delta = p_1 - p_2$, being p_1 and p_2 the proportion of success in the n_1 and n_2 patients randomised to DFP and DFX arms, respectively. Non-inferiority will be claimed if δ_L is greater than -0.125. The two sided 95% confidence interval for δ will be estimated based on asymptotic normal approximation for the difference of two binomial probabilities as follows:

$$(p_1 - p_2) \pm Z_{1-\alpha/2} \sqrt{Var(p_1 - p_2)}$$

where Z_γ is the γ^{th} percentile of the standardised normal distribution and

$$Var(p_1 - p_2) = p_1(1 - p_1)/n_1 + p_2(1 - p_2)/n_2$$

If non-inferiority of DFP to DFX is established based on the PP1 population and the confidence interval for the null hypothesis of non-inferiority based on the ITT population is similar or the percentage of success for DFP is greater than that of DFX in magnitude, the hypothesis that DFP is superior to DFX in terms of the defined success criteria will be tested at the one-sided alpha level of 0.025. Superiority testing will be based on the ITT population. The rationale for superiority is justified by the known beneficial effects of DFP at the cardiac level.

Secondary efficacy

Efficacy measured through serum ferritin levels

Serum ferritin will be analysed as secondary measure of treatment efficacy. Serum ferritin is a well validated and clinically widespread surrogate measure of iron load, highly correlated with iron in the liver. It represents an easy to assess parameter in the paediatric population.

Serum ferritin will be tested in terms of quantitative variable as part of the composite endpoint measurable in the entire experimental population. The purpose of this analysis is to clarify the interpretation of the primary composite endpoint and hence no adjustment for multiplicity will be considered. The population for this analysis is the PP2. ITT analysis will be used to corroborate the findings.

Non inferiority of DFP to DFX will be tested considering a non inferiority margin of 400 ng/mL.

Non-inferiority will be assessed based on the two sided 95% confidence interval $[\delta_L, \delta_U]$ of the difference $\delta = m_1 - m_2$, being m_1 and m_2 the mean difference between baseline and end of treatment assessments of DFP and DFX, respectively, and n_1 and n_2 the numbers of patients randomised to DFP and DFX arms. Non-inferiority will be claimed if δ_L is greater than -400 ng/ml.

The two sided 95% confidence interval for δ will be estimated as follows:

$$(m_1 - m_2) \pm Z_{1-\alpha/2} \sigma \sqrt{\frac{1}{n_1} + \frac{1}{n_2}}$$

where Z_γ is the γ^{th} percentile of the standardised normal distribution and σ^2 is the pooled variance.

Serum ferritin trends over the 1 year period of treatment will be also investigated. A repeated measures analysis of variance model with treatment-group as main effect will be fitted. The H_0 of equal between group regression slopes will be tested by evaluating whether the interaction between the categorical factor (treatment group) and the repeated measure (monthly measures of serum ferritins) equals zero, i.e. no interaction. The rejection of the null hypothesis on the interaction term (treatment group*monthly ferritin measure) will be supportive of different trends between DFP and DFX arms. The ITT population will be used for this analysis. Handling of missing data for this analysis is described in Section 11.4.

Descriptive statistics for trends in subgroups of patients according to age classes will be also provided.

Efficacy measured through cardiac T2* MRI

In the last years, the role of cardiac MRI T2* in the management of patients affected by hereditary haemoglobinopathies has been highlighted. Findings are available for the adult population, more limited experience is reported in children. Despite the importance of early detection of cardiac siderosis, MRI is difficult to perform in the paediatric population and it is usually uninformative in younger children (namely less than 10 years) due to late iron accumulation in the heart.

As a consequence, cardiac MRI T2* will be analysed as additional secondary measure of treatment efficacy in the subgroup of patients (over 10 years) for which the scan is available. It will be analysed as binary variable (successfully/unsuccessfully chelated patient according to the criterion 4.3.1 in Section 4.3) as part of the composite endpoint as well as according to its quantitative nature.

Due to the paucity of paediatric data on cardiac MRI T2*, descriptive statistics will be calculated and used to support efficacy conclusions. Descriptive measures will be listed by visit and treatment and characterised by frequency and percentage or mean, standard deviation, median, and quartiles.

However, considering the importance of improving knowledge on iron overload at the heart level in the paediatric population, a test for non inferiority of DFP to DFX in terms of cardiac MRI T2* (successfully/unsuccessfully chelated patient according to the criterion 4.3.1 in Section 4.3 Primary endpoint) will be performed whenever MRI evaluation will be available in at least 60-70% of the evaluable population. See section 11.3 different scenarios (non inferiority margins and sample size) related to this secondary efficacy assessment. The population for this analysis is the PP3.

Efficacy measured through MRI liver iron concentration

Iron overload in the liver compartment will be assessed as additional secondary measure of efficacy. LIC changes within one year will be evaluated in terms of percentage of successfully chelated patients according to the success criterium described in section 4.4.1 Secondary endpoints. LIC absolute values will be also analysed.

Considering the target population of the study, it is likely that patients undergoing cardiac MRI T2* will be also those patients able to perform R2 scan for LIC assessment. LIC measures are hence expected to be available in a subgroup of the experimental population. As a consequence LIC estimates as additional secondary measure of efficacy will be analysed only in terms of descriptive statistics. Descriptive measures will be listed by visit and treatment and characterised by frequency and percentage or mean, standard deviation, median, and quartiles. The population for this analysis is the PP3.

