In details, a composite outcome measure will be defined as primary endpoint of the study according to patient's age, as follows:

- in patients < 10 years of age treatment success will be defined only in terms of serum ferritin level (criterion A);
- in patients ≥ 10 years of age treatment success will be defined in terms of both serum ferritin level and cardiac MRI T2* (criteria A and B).

In patients ≥ 10 years of age who would require sedation for the MRI scan, treatment success will be defined only in terms of serum ferritin level (criterion A). Details on the choice of the composite outcome are in **Section 11.1**.

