6.6 Randomisation

Patients will be stratified before randomisation into two groups according to age (<10 years and \geq 10 years) considering their different capabilities in undergoing cardiac MRI T2*.

After stratification patients will be randomised on Day 0 of the study at the 1:1 ratio to one of two treatment groups. One group will be treated with DFP, the other (control) group with DFX.

Patients will be assigned a sequential patient number in each center at screening. Each patient will be unambiguously identified by a 6-digit subject identifier consisting of a 2-digit centre number and the 4-digit, sequential patient number. This subject identifier is unique and will not be changed throughout the entire study. Subject identification numbers of patients that did not meet the entrance criteria and were not randomised will not be re-used.

Randomisation will be determined centrally and balanced by country. The randomisation list will be printed out in advance at the start of the study. Since the number of recruited patients *per* centre cannot be determined *a priori*, a larger number of randomised numbers *per* country will be generated to allow a greater than anticipated number to be studied in the event that the enrolment rate in some specific centre is below expectations.

The randomisation number and the assigned treatment will be recorded in the source documents as well as in the CRF of the corresponding patient.

No fixed number of patients per age group will be specified upfront. However at least 10% of the patients recruited into the study will be aged from 1 month to less than 6 years.

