The choice of this composite endpoint allows the feasibility of the trial in the entire paediatric population and provides an up to date approach to the evaluation of the global iron accumulation in paediatric transfusion-dependent patients. In addition the use of a composite endpoint (rather than an alternative one) allows avoiding multiplicity while adequately characterising (total body iron load and in the heart) the beneficial effect of treatments.

Each component of the composite endpoint will be considered for secondary analyses with the intent to clarify the interpretation of the composite. For such analyses no adjustment for multiplicity will be foreseen (see **Section 11.2**).

Based on the above defined composite endpoint, non inferiority is established if the lower limit of two sided 95% confidence interval of the difference in success rate is above - 12.5%. The choice of this margin is based on clinical considerations starting from the available evidences for the effects of DFP and DFX on ferritin levels and cardiac iron load.

In details, the percentage of expected success for DFX and DFP measured as change from baseline to 1 year treatment is summarised in the following **Table 6**:

Table 6: Success rates for DFP and DFX

Serum ferritin levels	76% (95%CI: 63.6-88.5) DFP mean dose 66.4 mg/kg/day (Addis A et al, 1999) Paediatric population included in the meta-analysis but not analysed separately.	57% (95%CI: 50.7-63.3) DFX used at 20-30 mg/kg/day (Taher A et al, 2009) 75 adult and 162 paediatric patients
Cardiac MRI T2*	66% Higher percentage in splenectomised patients (Pennell DJ et al, 2006) 29 adults	69.5% in patients with moderate-to-mild baseline cardiac iron load (≥ 10 to <20 ms) DFX mean dose 33.1 \pm 3.7 mg/kg/day (Pennell DJ et al, 2010) 72 adult and 29 paediatric patients

Pooling together these findings, the expected percentage of success in the composite endpoint is assumed to be equal to 65% and 67.5% for DFX and DFP, respectively. The non inferiority margin of 12.5% has been considered to be a good estimate of an achievable lower bound of the true difference between the DFP and DFX.

Other secondary objectives include the evaluation of treatment efficacy in terms of liver iron concentration, the assessment of treatment safety and tolerability profiles, healthcare resources utilisation and patient global assessment and the analysis of the relationship of the demographic covariates and the disposition of DFP.

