Table 7. Sample size and power on cardiac MRI T2* (percentage of successfully chelated patients)

DFX/DFP Success (%)	65/70	65/70	70/75	70/75
Non inferiority margin (%)	-12.5	-10	-12.5	-10
Power (%)	80	75	80	75
n (per group)	112	135	102	123

On these calculations, a test for non inferiority in terms of percentage of successfully chelated patients according to the criterion 4.3.2 as defined in Section 4.3 Primary endpoint is considered feasible and supported by an adequate power whenever cardiac MRI T2* is available in about 60-70% of the evaluable population.

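### The primary interval leaves out age, although randomisation is stratified at 10 years and the success rule changes there; stratifying by age would recover a small amount of precision

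*Combined protocol and SAP*

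**What the plan says.** Section 6.6: "Patients will be stratified before randomisation into two groups according to age", with the cut at 10 years. The same section adds "Randomisation will be determined centrally and balanced by country" and fixes no numbers per age group.

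Section 4.3, repeated in section 11.1, judges patients under 10 on serum ferritin alone. From 10 years, "treatment success will be defined in terms of both serum ferritin level and cardiac MRI T2"*, except that older patients who would need sedation for the scan are judged on ferritin only.

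Section 11.6 takes PP1 as the primary population and ITT as support. The 95% interval for the difference in success proportions "will be estimated based on asymptotic normal approximation for the difference of two binomial probabilities as follows". Its variance is the sum of p(1-p)/n over the two arms, and n1 and n2 are described as patients randomised. The serum ferritin analysis in the same section repeats that description, although its population is PP2. For the superiority test on ITT, section 11.6 gives the alpha level but does not spell out the method. Age enters elsewhere only through subgroup and descriptive summaries, and the classes in section 11.3 (1 month to 5, 6 to 11, 12 to under 18 years) do not cut at 10.

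**The concern.** Age 10 is both a randomisation stratum and the point at which the endpoint becomes harder to meet: requiring two criteria can never be easier than requiring the ferritin criterion alone. If success differs between the strata, the crude variance includes between-stratum variation that stratified randomisation has already largely removed from the comparison. The interval is then wider than it needs to be.

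The sample size leaves no slack, so even a small gain is of use. PP1 is also formed after randomisation and needs complete endpoint data, which for most older patients includes MRI. The age mix of PP1 could therefore drift between arms. Stratifying removes that age component, but not other post-randomisation selection.

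A smaller, separate matter is the wording of n1 and n2. It names randomised patients, whereas the analyses use PP1 and PP2.

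**Working it through.** **Inputs from the documents.** Margin -12.5 points, one-sided alpha 0.025, 80% power, success 65% (DFX) and 67.5% (DFP), 310 evaluable, 20% dropout, 388 randomised (sections 4.1, 11.1, 11.12). Component rates from Table 6: ferritin 57% (DFX) and 76% (DFP); cardiac T2* 69.5% and 66%. Ferritin standard deviation 1000 ng/mL (section 11.12).

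**Assumptions.** A share f of 50 to 70% aged 10 or over, loss unrelated to age and arm, the same treatment difference in both strata, and a stated gap in success between strata. The documents give none of these. The 60-70% in section 11.12 ("whenever cardiac MRI T2* is available in about 60-70% of the evaluable population") is a condition for the separate T2* test and not an age split.

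**1. The plan's own figures.** Variance sum: 0.65×0.35 + 0.675×0.325 = 0.446875. n per arm = (1.960+0.842)² × 0.446875 / 0.15² = 155.9, so 156 per arm or 312, against the plan's 310. Power at 155 per arm is 79.8%. 310/0.8 = 387.5, so 388. Crude half-width: 1.96 × √(0.446875/155) = 10.52 points. The plan's figures reproduce.

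**2. Expected effect of stratifying.** With weights in proportion to stratum size,

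variance ratio = 1 - f(1-f)(gap_DFX² + gap_DFP²)/0.446875.

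For f = 0.5 and the same gap in both arms:
- 5 points: 1 - 0.25×0.005/0.446875 = 0.997; half-width 10.51
- 10 points: 1 - 0.25×0.02/0.446875 = 0.989; half-width 10.47
- 17.4 points: 1 - 0.25×0.0606/0.446875 = 0.966; half-width 10.34
- 25.8 points: 1 - 0.25×0.1331/0.446875 = 0.926; half-width 10.12

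**3. Simulation.** 400,000 trials per cell, 194 per arm split by age, each patient kept with probability 155/194. Crude Wald interval against Mantel-Haenszel with Sato variance. Power is at a true difference of +2.5 points, error at -12.5.

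| Gap (points) | Aged ≥10 | Power crude | Power stratified | Gain (points) | Error crude | Error stratified |
|---|---|---|---|---|---|---|
| 0 | 50% | 79.9% | 79.8% | about 0 | 0.0248 | 0.0248 |
| 10 | 50% | 79.9% | 80.2% | 0.3 | 0.0241 | 0.0244 |
| 17.4 | 50% | 80.2% | 81.2% | 1.0 | 0.0235 | 0.0251 |
| 25.8 | 50% | 80.6% | 82.8% | 2.2 | 0.0217 | 0.0250 |
| 17.4 | 70% | 80.1% | 80.9% | 0.8 | | |
| 25.8 | 70% | 80.4% | 82.3% | 1.9 | | |

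Allowing for simulation error, the gains are about 0 at 5 points or less, 0.2 to 0.3 at 10, 0.8 to 1.0 at 17 and 1.9 to 2.3 at 26. They are a little smaller than the formula suggests, because stratified randomisation also makes the crude interval slightly conservative, and its power rises with the gap.

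**4. Where 17 and 26 come from.** If the two criteria were independent, older patients would succeed in 0.57×0.695 = 39.6% (DFX) and 0.76×0.66 = 50.2% (DFP). Those rates lie 57 - 39.6 = 17.4 and 76 - 50.2 = 25.8 points below the ferritin-only rates.

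These inputs do not fit the planning rates. With half aged 10 or over, Table 6 under independence gives 0.5×57 + 0.5×39.6 = 48.3% (DFX) and 0.5×76 + 0.5×50.2 = 63.1% (DFP), not 65% and 67.5%. Conversely, an overall 65% with a 17.4-point gap needs 65 + 0.5×17.4 = 73.7% under age 10 on DFX. The Table 6 interval is 50.7 to 63.3%.

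**5. n1 and n2 in the ferritin analysis.** Half-width = 1.96 × 1000 × √(2/n): 222.6 ng/mL at n = 155 (analysed) and 199.0 ng/mL at n = 194 (randomised).

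**The case against.** The strongest reply is that the plan pre-specifies a valid interval that matches the way the trial was sized, so this is a preference. That stands in part: nothing in section 11.6 is wrong, and the gain is nil when the strata succeed equally often. Nor is the change strictly without downside. When the treatment difference was allowed to vary between strata by 10 or 20 points (gaps of 17.4 and 25.8, overall +2.5 kept), the change in power ran from -0.2 to +4.1 points.

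The second reply is that the larger gaps are speculative, and this stands. Step 4 shows the mismatch with the planning rates. Taken consistently, Table 6 under independence with half aged 10 or over gives power of 99.8% crude and 99.9% stratified. The DFX T2* rate is "69.5% in patients with moderate-to-mild baseline cardiac iron load", whereas criterion B in section 4.3.1 also accepts stability or a small fall when baseline is 20 ms or more. Late cardiac iron loading in children, the sedation exception and positive correlation between the criteria would all tend to shrink the gap.

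Two stronger readings are tempting. One is that omitting the stratum inflates the primary type I error. The documents and the calculation do not support it: with loss unrelated to age and arm, the crude error stays at or below 0.025. The other is that the ferritin interval will be computed with 194 per arm, which would raise its one-sided error to 0.040. That is the literal wording, but section 11.6 names PP2 as the population, section 11.2 restricts PP2 to patients with both ferritin values, and section 11.12 sizes the analysis on 310 evaluable patients.

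**Conclusion.** The point holds as a modest improvement in precision. The plan stratifies on a factor that also determines the endpoint definition, then leaves it out of the confirmatory interval without giving a reason. Under the assumptions listed, the supportable gain is about 0 to 2 points of power, with the one-sided error of the stratified interval at 0.024 to 0.025. The upper end depends on gaps between strata that the documents do not establish. The sample size is not called into question.

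The n1/n2 wording needs clarification only. The intended denominators can be read from the other sections.

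**What to change.** - In section 11.6, pre-specify as primary the Mantel-Haenszel risk difference stratified by age (<10, ≥10 years) with a 95% interval from the Sato variance, on PP1 and against the same -12.5-point margin. With 1:1 allocation the weights are close to proportional to stratum size, so the target remains essentially the overall difference.
- Use the same method for the supporting ITT analysis and for the ITT superiority test. Report the crude interval as a sensitivity analysis.
- Put country in a pre-specified sensitivity analysis only. Adding it to the primary analysis when cell sizes permit would make the confirmatory method depend on the data.
- In the primary and ferritin parts of section 11.6, define n1 and n2 as the patients analysed in the respective population (PP1, PP2 or ITT), by assigned arm.

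The cost is SAP wording and a few lines of code. No extra data or patients are needed, but the change must be made before outcome data are examined.

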4.3.1 Definition of successful chelation

The following criteria will be used to identify a treatment success:

- Criterion A - Serum Ferritin Levels:** success for patients with baseline serum ferritin levels of 2500 ng/mL or more will be defined as a 20% reduction or more after 1 year treatment. Success for patients with baseline serum ferritin levels less than 2500 ng/mL will be defined as any decrease in serum ferritin, or an increase in serum ferritin, if that increase is less than or equal to 15% of the baseline level, as long as the increase does not result in a serum ferritin above 2500 ng/mL within 12 months despite continual transfusional therapy.
- Criterion B - MRI T2* Cardiac Iron Concentration:** success for patients with baseline values of 20 ms or more will be defined as any increase in T2* or, if there is a decrease, the decline is not more than 10% after 1 year, as long as this does not result in a value below 20 ms. Success in patients with a baseline less than 20 ms will be defined as an increase in T2* of 10% or more despite transfusional therapy.

Table 1 summarises the applied criteria.

Table 1. Definition of treatment success

Baseline ferritin \geq 2500 ng/mL	Reduction of 20% or more after 1 year treatment
Baseline ferritin $<$ 2500 ng/mL	
 any decrease increase \leq 15% as long as the increase doesn't result in ferritin $>$ 2500 ng/ml after 1 year treatment
Baseline MRI T2* $<$ 20 ms	
 Increase of 10% or more after 1 year treatment
Baseline MRI T2* \geq 20 ms	
 any increase decrease \leq 10% after 1 year treatment as long as the decrease does not result in MRI T2* value $<$ 20 ms

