11.12 Sample Size and power considerations

Primary efficacy objective

Assuming type I and type II errors of 0.025 and 0.20, respectively, and a one-sided test, and under the assumptions that the expected proportion of subjects declared treatment successes in the DFX arm is 65%, and the expected proportion of subjects declared treatment successes in the DFP arm is 67.5% a sample size of 310 subjects, randomized in a 1:1 ratio to DFP or DPX will yield 80% power to demonstrate non-inferiority of DFP versus DFX. Taking into account a possible dropout rate of about 20% a total enrolment of 388 patients aged from 1 month to less than 18 years are expected to be included in the trial.

Secondary efficacy objective

Sample size requirements for the secondary efficacy objectives (non-inferiority in terms of ferritin levels and cardiac MRI T2*) are provided in the following.

Based on published literature, testing for non-inferiority is appropriate also when comparing DFP to DFX efficacy in terms of serum ferritin levels. In this case, considering a hypothesis testing on the continuous measure, a non inferiority margin of 400 ng/ml is considered a reliable estimate of the true allowed maximum difference between the IMPs in order to assume DFP to be non-inferior to DFX in controlling iron overload in patients affected by hereditary haemoglobinopathies. The standard deviation of the differences is available by pooling findings from paediatric studies conducted in Europe and outside (El Alfay M et al., 2010), and a reliable and conservative estimate can be 1000 ng/mL.

On these assumptions, 310 evaluable patients are sufficient to provide at least 90% power to demonstrate non inferiority of DFP to DFX, assuming a type I error of 0.025 and a one-sided test.

When considering efficacy in terms of cardiac MRI T2*, less reliable estimates of treatment efficacy are available, especially in the paediatric population. However, there are no reasons for not assuming at least a non inferiority of DFP to DFX, considering also the known beneficial effects of DFP at the cardiac level. Based on the limited published figures of cardiac MRI T2* in the paediatric population and taking into account adult data, some plausible scenarios of sample sizes and related powers are provided in the following **Table 7**, assuming a type I error of 0.025 and a one-sided test. Detailed power curves will be provided in the statistical plan.

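### The success hurdle changes at baseline ferritin 2500 ng/mL, but the primary interval ignores ferritin class: a valid analysis that gives up precision and leaves a single trial open to chance imbalance

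*Combined protocol and SAP*

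**What the plan says.** Criterion A in section 4.3.1 applies to every patient and has two tiers. In the upper tier, "success for patients with baseline serum ferritin levels of 2500 ng/mL or more will be defined as a 20% reduction or more". Below 2500 ng/mL, any fall counts as success, and so does a rise of up to 15% that does not take ferritin above 2500. A child whose ferritin falls by 10% therefore fails in one tier and succeeds in the other.

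Section 6.6 names one stratification factor: "Patients will be stratified before randomisation into two groups according to age", cut at 10 years. It adds balancing by country. Ferritin is not mentioned there.

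The primary analysis in section 11.6 compares the two success proportions in the per-protocol population PP1. The interval is "estimated based on asymptotic normal approximation for the difference of two binomial probabilities", with variance p1(1-p1)/n1 + p2(1-p2)/n2. No covariate or stratum enters it. Non-inferiority is claimed if the lower 95% limit lies above -12.5 points. The subgroup analyses in section 11.3 are by age only. No section stratifies, adjusts or runs a sensitivity analysis by baseline ferritin class.

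**The concern.** When the definition of success itself depends on a baseline value, that value is a natural candidate for a prognostic factor. If success rates differ between the two ferritin classes, two things follow for the crude comparison.

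- An excess of one class in one arm moves that trial's observed difference even when the drugs are equal.
- Variation between classes stays in the standard error, although a stratified analysis would remove it.

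The trial is decided at one lower limit and sized with no slack over 80% power, so modest precision can matter. It is open label (section 6.5), so an adjustment chosen after an imbalance has been seen would be open to challenge. That is the reason to settle it in advance.

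**Working it through.** **Inputs from the protocol.** Section 11.12: "Assuming type I and type II errors of 0.025 and 0.20, respectively, and a one-sided test"; success 65% on DFX and 67.5% on DFP; "a sample size of 310 subjects, randomized in a 1:1 ratio to DFP or DPX will yield 80% power"; "a possible dropout rate of about 20% a total enrolment of 388 patients". Margin 12.5 points (sections 4.1 and 11.6).

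**Inputs assumed, because the protocol does not give them.** Share of patients at 2500 ng/mL or more: q = 30% or 50%. Gap in composite success between the classes: g = 10, 20, 30 or 40 points, the same in both arms.

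**1. Reproduce the plan's figure.** Variance sum V = 0.65×0.35 + 0.675×0.325 = 0.446875. The distance from the margin is 0.125 + 0.025 = 0.15. Required n per arm = V(1.960 + 0.842)²/0.15² = 155.9, so 156 per arm or 312 in total, against 310 stated. With 155 per arm, SE = √(0.446875/155) = 0.0537 (5.4 points), the 95% half-width is 10.5 points, and power = Φ(0.15/0.0537 − 1.96) = 79.8%. Enrolment: 310/0.80 = 387.5, so 388. The plan's size and its crude analysis agree.

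**2. Precision gained by stratifying on class.** The variance sum falls by 2q(1−q)g². Power = Φ(0.15/√[(V − 2q(1−q)g²)/155] − 1.96).

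**3. Effect of chance imbalance.** The standard error of the between-arm difference in the share is √(2q(1−q)/155), which is 5.2 points at q = 30% and 5.7 points at q = 50%. The crude difference moves by g times the imbalance.

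| Gap g | Variance reduction | Power at 155 per arm | Shift from a 1-SE imbalance |
|---|---|---|---|
| 10 points | 0.9-1.1% | 80.1-80.2% | 0.5-0.6 points |
| 20 points | 3.8-4.5% | 81.3-81.5% | 1.0-1.1 points |
| 30 points | 8.5-10.1% | 83.1-83.8% | 1.6-1.7 points |
| 40 points | 15.0-17.9% | 85.8-86.9% | 2.1-2.3 points |

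Each range runs from q = 30% to q = 50%. Example (q = 0.5, g = 0.3): the reduction is 2×0.25×0.09 = 0.045, and 0.045/0.446875 = 10.1%.

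**4. Simulation check** (200,000 trials per scenario, crude Wald against a Mantel-Haenszel-weighted risk difference).

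- The crude estimate averages the true 2.5 points.
- One-sided type I error at the margin is 0.0246-0.0256 crude and 0.0251-0.0259 stratified.
- Power is 79.8-79.9% crude, and 80.3-80.5%, 81.5-81.9%, 83.4-83.9% and 86.1-87.1% stratified at the four gaps.
- At gaps of 20, 30 and 40 points the two methods reach different non-inferiority conclusions in about 4.5-5%, 7-8% and 9.5-10.5% of trials. Most of these are a crude failure where the stratified analysis succeeds.

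The calculations cover ferritin class alone. The effect of adding the age stratum was not computed.

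**The case against.** The strongest reply is that nothing here is wrong. Under randomisation the crude interval is valid, and its standard error already contains chance imbalance in ferritin class. Imbalance and lost precision are one source of variation described twice. That stands. A reader might infer that the primary result is biased or that the trial is underpowered. Neither is supported: the estimate is unbiased over repeated trials, type I error is nominal, and the planned power is delivered.

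Second, the size is assumed. This also stands. Quoting only gaps of 20 points or more would flatter the proposal, and the top figure needs about 86% against 46% success (66.25% plus or minus 20 points). Setting the shift against the 12.5-point margin also flatters it. Against the crude SE of 5.4 points, a one-standard-error imbalance is worth 0.1 to 0.4 SE.

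Third, a stricter hurdle does not prove lower success. Several provisions could narrow the gap or alter it:

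- section 6.2 links an optional higher DFX starting dose to ferritin above 2500;
- section 6.3 allows increases in either drug when stable ferritin exceeds 1500, and Table 4 requires reductions at 500 or below;
- criterion B applies as well in scanned patients of 10 years or more;
- premature discontinuation counts as failure (sections 9 and 11.13).

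The direction is therefore undocumented. But the precision gain depends on g², so it does not matter which class does better.

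Two limits remain. Two classes do not remove imbalance within a class. Criterion B has the same two-tier form at 20 ms, which this proposal does not address.

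**Conclusion.** The point holds as a missed efficiency: a plausibly prognostic baseline class, built into the endpoint definition and already measured, is left out of both randomisation and the primary analysis. It is not an error, a systematic bias or a shortfall in planned power.

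The benefit ranges from negligible (power 80.1-80.2% against 79.8%) at a 10-point gap to material (85.8-86.9%) at 40 points. It rests on an assumed 30-50% share at or above 2500 ng/mL, a gap common to both arms, and 155 evaluable patients per arm. The protocol can neither confirm nor exclude any of these gaps.

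The validity statement concerns the randomised comparison. PP1 is defined after randomisation (section 11.2), so imbalance in that set need not be due to chance alone, and adjusting for ferritin class would not by itself cure selection.

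**What to change.** Amend section 11.6 before database lock, as follows.

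- **Estimator.** Keep the marginal risk difference, the -12.5 point margin and the two-sided 95% interval. Estimate the difference by Mantel-Haenszel weighting or standardised logistic regression, naming one with its variance formula. Adjust for baseline ferritin class (<2500, >=2500 ng/mL, central V3 value) and the age stratum used in randomisation (<10, >=10 years).
- **Sensitivity.** Report the present crude interval alongside.
- **Description.** Tabulate success by ferritin class and arm.
- **ITT patients without a central V3 ferritin.** Section 11.6 counts them as failures, but they would have no class. Classify them by the local V1 screening value and still count them as failures.

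Central ferritin at V3 is already planned (section 7.3.12), so no new data are needed. The cost is a written protocol amendment, which section 18.2 requires for any change to the protocol, with ethics approval if the change is judged to affect scientific quality significantly. There is also slightly more analysis work. If the two classes have similar success rates, little is gained.
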